5.2.2 AE Relatedness and Severity

For all AEs, the PI ([name]) will use his best judgment and indicate how related the AE is to the research procedures and intervention. He will assign the AE to one of the four categories below:

- **Definitely related:** The AE *is clearly related* to the intervention
- **Probably related:** The AE *is likely related* to the intervention
- **Possibly related:** The AE *may be related* to the intervention
- **Unlikely to be related:** The AE *is doubtfully related* to the intervention
- **Definitely not related:** The AE *is definitely not related* to the intervention

The PI will provide an AE severity:

- **Mild:** asymptomatic or mild symptoms; clinical or diagnostic observations only; no intervention indicated
- **Moderate:** minimal, local, or noninvasive intervention indicated
- **Severe:** Severe or medically significant, but not immediately life-threatening; hospitalization or prolongation of hospitalization indicated; disabling
- **Life-threatening:** Life-threatening consequences; urgent intervention indicated
- **Fatal**

The PI will AE level of expectedness:

- **Unexpected adverse events:** (i.e., has NOT been addressed or described in one or more of the following: informed consent document for this study, IRB application for this study, grant application or study agreement, protocol or procedures for this study, investigators' brochure or equivalent (for FDA regulated drugs or devices), DSMB/DSC Reports, published literature, other documentation)

- **Expected adverse events:** (i.e., has been addressed or described in one or more of the following: informed consent document for this study, IRB application for this study, grant application or study agreement, protocol or procedures for this study, investigators' brochure or equivalent (for FDA regulated drugs or devices), DSMB/DSC Reports, published literature, other documentation, or characteristics of the study population.

5.2.3 IRBMED Reporting

AEs, SAEs, UaPs and protocol deviations will be reported to IRBMED following IRBMED reporting guidelines.

5.3 CRITERIA OF INTERVENTION DISCONTINUATION

If the subject experiences any SAE that might be considered related to Mi-Kristal participation, the study coordinator will inform the subject to stop all intervention activities. The PI will decide whether to continue study activities thereafter. Every effort will be made to maintain the subject's participation in follow-up activities. If lactulose therapy is terminated before 28 days, the Day 28 outcome assessments will be collected within 5 days of lactulose termination.

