1.2 END POINTS

All patients will be followed until death, liver transplantation or final study visit at 28 days post – enrollment.

Primary Endpoint

1. Comparison of SF-8 at 28 days post-baseline, between the two groups.

Secondary Endpoints

1. Comparison of ANT, overall sleep quality, regular daily activity impairment, falls, and average number of daily bowel movements at 28 days, compared between the two groups.

[figure not shown]

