4.6 DISTINCT CLINICAL SCENARIO: PATIENT HOSPITALIZATION

In the event of a subject's hospitalization during the study period, we will record the event as an Adverse Event (AE). If the subject's hospitalization coincides with study activities, we will revise each procedure as follows:

- 1) Lactulose therapy:** If a subject in the treatment group is hospitalized at Michigan Medicine during the study, the study PI and/or coordinator will contact the Michigan Medicine care team to discuss continuation of lactulose therapy during the hospitalization. If the hospitalization is a result of an AE from lactulose use, this will be discussed with the PI and lactulose may be paused or discontinued.
- 2) Follow-up phone study visits:** If the hospitalization coincides with the Day 28 follow-up visit, we will provide the subject an opportunity to reschedule the visit after discharge, under PI discretion.

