4.7 DISTINCT CLINICAL SCENARIO: OVERT HE DIAGNOSIS & INITIATION OF LACTULSOE THERAPY

If a subject in either group (treatment or control) is diagnosed with Overt HE, or prescribed lactulose for any clinical reason outside of study participation during the study period, their participation in the study will be terminated. An early termination visit will be conducted with the subject to collect outcome data including the SF-8, ANT and Follow-Up Health Questionnaire.

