4.8 EARLY TERMINATION VISIT

If a subject discontinues participation in the study, the subject will be asked to complete all 28 Day Follow Up Assessments at the time of discontinuation including the SF-8, ANT and Follow-Up Health Questionnaire. If they choose not to complete them, their participation will be terminated immediately. All data collection prior to termination will be retained by the study team.

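### Sections 5.3 and 4.7 take the Day 28 outcomes early after certain events, with no later SF-8 scheduled and no rule for analysing the early values

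*Combined protocol and SAP*

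**What the plan says.** The general rule is in Sections 1.2 and 4.4. Section 1.2 states: "All patients will be followed until death, liver transplantation or final study visit at 28 days". Stopping lactulose, overt HE and outside lactulose are not listed as ends of follow-up. The primary endpoint is "Comparison of SF-8 at 28 days post-baseline, between the two groups". Section 4.4 sets the visit at Day 28±5 and applies the SF-8, the ANT and the Health Follow-Up Questionnaire to all subjects.

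Two later sections re-time those outcomes after particular events.

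- **Section 5.3** (possible only in the lactulose arm): "If lactulose therapy is terminated before 28 days, the Day 28 outcome assessments will be collected within 5 days of lactulose termination". The sentence before it reads: "Every effort will be made to maintain the subject's participation in follow-up activities". It names no visit or instrument.
- **Section 4.7** (either arm): "If a subject in either group (treatment or control) is diagnosed with Overt HE", or is prescribed lactulose outside the study, participation ends. "An early termination visit will be conducted with the subject to collect outcome data including the SF-8, ANT and Follow-Up Health Questionnaire".

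Section 4.8 covers subjects who discontinue participation: "the subject will be asked to complete all 28 Day Follow Up Assessments at the time of discontinuation". That is a lesser case, because those subjects are leaving the study. Section 4.6 handles a hospital stay that coincides with the Day 28 visit differently: "we will provide the subject an opportunity to reschedule the visit after discharge, under PI discretion".

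Section 5.1 lists outcomes collected outside the window among possible protocol deviations. Section 6.2 names MANOVA and multiple linear regression and says nothing about values taken early.

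**The concern.** When the timing of the primary outcome depends on an event after randomization, the arms may no longer be compared at the same point. Here one trigger exists only in the lactulose arm. The other may also occur unequally: the Significance section says the trial enrols patients at high risk of overt HE, and Section 8.3 lists a lower risk of HE as a possible benefit. Section 2 gives controls no placebo, so subjects know their arm when they rate their own health.

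The plan also leaves open whether an early value is the Day 28 endpoint, a missing value or a deviation. If that is settled after the data are seen, the choice can be questioned. The same gap affects Section 2, which aims for 50 subjects who complete and enrols up to 75. It does not say whether a Section 4.7 or 5.3 subject counts as a completer.

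**Working it through.** The plan gives no figure on this point to reproduce. The check is a count of days.

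**Inputs.** The window is Day 28±5, that is Days 23-33 (Section 4.4). The assessment falls within 5 days of stopping (Section 5.3). The SF-8 looks back 4 weeks, taken as 28 days (Appendix C). The WPAI item looks back 7 days, and falls are counted since enrolment (both in the Health Follow-Up Questionnaire). Assumptions: drug is taken from Study Day 1 to stop day *s* without gaps, and the visit day *a* is the last day of the recall.

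**Step 1: in or out of the window.** The Section 5.3 visit lies between *s* and *s*+5.

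- Always early: *s*+5 < 23, so *s* = 1-17.
- Possibly early: *s* < 23 ≤ *s*+5, so *s* = 18-22.
- In the window: *s* = 23-27, where the latest visit is 27+5 = Day 32, before Day 33.

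These are calendar positions and not a rate of stopping.

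**Step 2: what the SF-8 recall contains.** The recall covers Days *a*−27 to *a*. For *s* ≤ *a* ≤ 28 it holds 28−*a* days before treatment, *s* on-drug days and *a*−*s* days after the stop. For *a* = 29-33 it starts on Day *a*−27, so the on-drug days are max(0, *s*−(*a*−28)). For a stop on Day 7:

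| Visit day | Before treatment | On drug | After stop |
|---|---|---|---|
| 8 | 20 | 7 | 1 |
| 12 | 16 | 7 | 5 |
| 28 | 0 | 7 | 21 |
| 33 | 0 | 2 | 26 |

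Up to Day 28, early timing leaves the on-drug days unchanged and exchanges post-stop days for pre-treatment days. After Day 28 the earliest on-drug days drop out. At Day 33 the recall is Days 6-33, so a Day 7 stop leaves 7−5 = 2 on-drug days and stops on Days 1-5 leave none.

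**Step 3: the other measures.** The WPAI recall covers Days *a*−6 to *a*. For a Day 7 stop it holds 6 on-drug days at Day 8 (Days 2-7), 2 at Day 12 (Days 6-7) and 0 at Day 28. Falls are counted over 28−*a* fewer days than at Day 28: 20 fewer at Day 8 and 16 fewer at Day 12. No proportion is given for falls, because after remote enrolment up to two weeks may pass before Kristalose is received (Section 4.3.1).

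**Step 4: is a later SF-8 scheduled?** Section 4.4 covers all subjects, and Section 5.3 intends to keep subjects in follow-up. A second set of outcomes at Day 28±5 would satisfy both. However, Section 5.3 speaks of the Day 28 assessments themselves being collected near the stop, which reads as moving them, and Section 4.7 ends participation. Neither section, nor Table 1, provides for two sets.

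**The case against.** The strongest reply is that specific rules override general ones. Sections 4.5 to 4.7 are headed as distinct scenarios, and Sections 4.7 and 5.3 each state a trigger and their own timing. That stands: they read most naturally as exceptions to Section 4.4. It does not settle how Section 6.2 treats the resulting values, or why Section 5.1 lists out-of-window outcomes as possible deviations.

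A second reply is that few subjects may be affected. This also has force. An SAE under Section 5.2.1 requires death or permanent disability definitely related to participation, and Section 4.3.1 reduces the dose for frequent bowel movements or worrying symptoms before any stop. Against that, the last sentence of Section 5.3 covers any early stop, and Section 4.6 allows discontinuation after a hospitalization caused by lactulose.

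A third reply is that a value taken at the stop answers a legitimate while-on-treatment question. It can, but the plan does not pose that question, and Section 1.2 names the 28-day comparison.

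A reader might infer that early assessment dilutes the effect and costs power. The documents do not support that: up to Day 28 the on-drug days in the SF-8 recall are the same, and no stopping rate or 28-day HE rate is given. A reader might also count each affected subject as 1/25 = 4% of an arm. But about 25 per arm is a target for completers, with up to 75 enrolled, and whether these subjects are among the 25 is unstated.

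**Conclusion.** The point holds as a fault in outcome timing and analysis that should be corrected. Followed as written, Sections 4.7 and 5.3 make the timing of the primary outcome depend on clinical events, and under Section 5.3 on arm. No Day 28±5 value is scheduled afterwards, and no rule covers the early one. A flat contradiction would be too strong a reading, because the sections work as exceptions that are not carried through to Sections 1.2, 5.1 and 6.2.

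The certain part is the calendar: stops on Days 1-17 always miss the window. For the SF-8 the shift is between pre-treatment and post-stop days in the recall. For WPAI and falls, the on-drug content or the counting period itself changes. The day counts rest on continuous dosing from Study Day 1 and a recall that ends on the visit day. The number of subjects affected and the size and direction of any bias cannot be derived from the documents and may be small.

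**What to change.** Reconcile Sections 4.7 and 5.3 with Sections 1.2 and 4.4, leaving every treatment decision as it is.

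- Also seek the SF-8, ANT and Health Follow-Up Questionnaire at Day 28±5 from every randomized subject who still consents.
- Keep the early visit, including the Section 4.8 exit visit, as a separately labelled and dated assessment.
- In Section 6.2, make the Day 28±5 value, analysed by randomized arm, the primary endpoint, and use early values in a sensitivity analysis.
- State whether Section 4.7 and 5.3 subjects count toward the 50 completers in Section 2.
- Report early stops, overt HE and outside lactulose by arm.

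The cost is an IRB-approved amendment (Section 8.4) and one extra remote contact per affected subject, with a call for the timed ANT. The trade-off is that the estimate will include some off-drug or rescued time, with fewer on-drug recall days at visits after Day 28. Aiming for Day 28 itself within the window limits that last loss.

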6. STATISTICAL CONSIDERATIONS

6.1 SAMPLE SIZE AND ACCRUAL

While no studies of lactulose enrolling patients exclusively with deficits in quality of life, one high quality study of lactulose therapy have been performed for patients with cognitive dysfunction defined by psychometric testing. Lactulose was associated with a 6.81 95%CI (5.2-8.4) point or 65% relative improvement in health-related quality of life using the Sickness Impact Profile compared to control. Given this magnitude of effect, very few patients need to be enrolled. However, if we hypothesize an attenuated effect (30% improvement), seeking to enroll with a 1:1 randomization, assuming an alpha of 0.05, we will have 90% power to detect a difference among 42 subjects. We will therefore proceed with a study of 50 patients to allow for additional adjustment of baseline covariates and drop-outs.

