1.1 SPECIFIC AIMS

1.1.1 Primary Aim

Aim 1: To determine whether lactulose therapy improves self-reported HRQOL as assessed using the Short Form-8 Health Survey (SF-8).

1a. Comparison of SF-8 scores from baseline to 28 days, between the intervention and control arm.

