4. STUDY INTERVENTIONS AND PROCEDURES

4.1 ASSESSMENTS

4.1.1 Baseline Assessments

1. Demographics Questionnaire (DQ) (Appendix A)

Participants will be asked to provide the following demographic information:

1. Sex
2. Age
3. Ethnicity
4. Race
5. Highest education level attained
6. Marital status
7. Occupation status
8. Income
9. Rural/Urban residence

2. Health History Questionnaire (HHQ) (Appendix B)

Participants will be asked to provide the following information:

1. Cause of cirrhosis
2. History of liver cancer
3. Liver transplant waitlist status
4. Driving status
5. Disability status (Katz-ADL)
6. Hospitalization within past 90 days
7. Emergency Room visit within past 90 days
8. Ascites status
9. Currently taking diuretics
10. Paracentesis within past 90 days
11. Hepatic encephalopathy status
12. Medications taken for HE
13. Dialysis status
14. Diabetes status
15. Congestive heart failure status
16. Chronic obstructive pulmonary disease status
17. Overall sleep quality (*PSQI*)
18. Falls in past 4 weeks
19. Average number of bowel movements per day

3. Short Form-8 Health Survey (SF-8) (Appendix C)

The SF-8 is an abbreviated version of an original 36-item health survey (SF-36). It is a generic multipurpose quality of life instrument. It contains psychometrically based physical and mental

health summary measures. The eight domains include general health, physical functioning, role physical, bodily pain, vitality, social functioning, mental health and role emotional.

4. Animal Naming Test (ANT) (Appendix D)

The animal naming test is a timed test that consists of subjects listing as many unique animals as possible in 60 seconds. This is a validated test used for the assessment of hepatic encephalopathy.

5. Alcohol Use Disorders Identification Test-C (AUDIT-C) (Appendix E)

The AUDIT-C is a brief 3-item alcohol screening instrument that reliably identifies persons who are hazardous drinkers or have active alcohol use disorders.

4.1.2 28-Day Follow-Up Assessments

1. Health Follow-Up Questionnaire (HFUQ) (Appendix G)

Participants will be asked to provide the following information:

1. Hospitalizations during study period
2. Overall sleep quality (PSQI)
3. Falls during study period
4. Average number of bowel movements per day
5. Ability to do regular daily activities (WPAI)

2. Short Form-8 Health Survey (SF-8) (Appendix C)

3. Animal Naming Test (ANT) (Appendix D)

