6.2 QUANTITATIVE ANALYSIS

We will compare differences in all outcomes, each continuous variable, using MANOVA. Multiple linear regression will be used to adjust for baseline covariates.

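### Section 6.1's 90% power with 42 subjects is unsupported for the SF-8 (though not shown false), and Section 6.2 designates no test of the SF-8

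*Combined protocol and SAP*

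**What the plan says.** - **Endpoint.** Section 1.2 gives the primary endpoint as "Comparison of SF-8 at 28 days post-baseline, between the two groups". Aim 1a in Section 1.1.1 words it as "Comparison of SF-8 scores from baseline to 28 days, between the intervention and control arm". Section 4.1.1 says of the SF-8 that "It contains psychometrically based physical and mental" health summary measures, and lists eight domains. No section names one score as primary.
- **Power.** Section 6.1 cites one study, in patients with cognitive dysfunction on psychometric testing. Its effect was 6.81 points (95% CI 5.2 to 8.4), a "point or 65% relative improvement in health-related quality of life using the Sickness Impact Profile compared to control". The section then assumes an attenuated effect of 30% and concludes, for 1:1 allocation, "assuming an alpha of 0.05, we will have 90% power to detect a difference among 42 subjects". This is raised to 50 for covariate adjustment and drop-outs.
- **Analysis.** Section 6.2 has two sentences: "We will compare differences in all outcomes, each continuous variable, using MANOVA" and "Multiple linear regression will be used to adjust for baseline covariates". Neither is linked to the power figure or designated as the test of Aim 1. The other endpoints in Section 1.2 include "falls, and average number of daily bowel movements at 28 days, compared between the two groups".
- **Numbers.** In Section 2, 50 means completers, about 25 per arm, with up to 75 enrolled.

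**The concern.** A power statement applies to one score, one difference, one SD and one test. Section 6.1 borrows its effect from another instrument, in patients selected differently, and gives no SD. It does not show how a 30% improvement translates to the SF-8, so a reader cannot tell what SF-8 difference the trial is designed to detect.

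Section 6.2 does not fill the gap. A joint test of all outcomes asks whether the arms differ on anything, and one of those outcomes is bowel frequency, which a laxative is expected to change. Without a named SF-8 score and test, neither the 90% nor a significant MANOVA can be read as an answer to Aim 1.

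**Working it through.** **Inputs from the documents:** alpha 0.05, power 90%, 42 subjects (21 per arm), 50 completers (25 per arm), SIP effect 6.81 points (CI 5.2 to 8.4) or 65%, assumed effect 30%. **Not given:** SF-8 difference, SD, sidedness, the test behind the 42, the cited study's arm sizes. **Assumed here:** two-sided test, equal SDs, baseline-to-day-28 correlation r of 0.3, 0.5 or 0.7.

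**1. Can the 42 be reproduced?** Not for the SF-8, because there is no difference or SD to enter. On the SIP it can only be approached, by taking the SD from the CI half-width of (8.4 − 5.2)/2 = 1.6. For an assumed m per arm in the cited study, SD = (1.6 / t(0.975, 2m − 2)) × √(m/2), which is 2.50, 2.81, 3.10 and 3.35 at m = 20, 25, 30 and 35. The 30% can be read in three ways. Total N for 90% power (two-sample t-test):

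| Reading of 30% | Points | m = 20 | m = 25 | m = 30 | m = 35 |
|---|---|---|---|---|---|
| 30% relative improvement: 6.81 × 30/65 | 3.14 | 30 | 36 | 44 | 50 |
| 30% of the cited effect: 6.81 × 0.30 | 2.04 | 66 | 82 | 100 | 116 |
| Cited effect cut by 30%: 6.81 × 0.70 | 4.77 | 14 | 18 | 20 | 24 |

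So 42 is attainable on the SIP under the first reading with about 30 per arm in the cited study. Under the second reading it is too few, and under the third more than enough.

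**2. What the 42 requires of the SF-8.** Let d be the between-arm difference divided by the SD. Power comes from a noncentral t with 2n − 2 degrees of freedom and noncentrality d√(n/2). Solving for 90% at n = 21 gives d = 1.025. The normal approximation gives (1.960 + 1.282) × √(2/21) = 1.00. A one-sided t-test would need 0.92.

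**3. What 50 completers can detect.** At n = 25, unadjusted, 90% power needs d = 0.936 and 80% needs 0.809. With adjustment for baseline SF-8, d is divided by √(1 − r²), one degree of freedom is lost, and the noncentrality is reduced for chance imbalance in the baseline score:

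| r (assumed) | d for 90%, 25 per arm | Rounded up |
|---|---|---|
| 0.3 | 0.903 | 0.91 |
| 0.5 | 0.820 | 0.82 |
| 0.7 | 0.676 | 0.68 |

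Ignoring chance imbalance gives 0.89, 0.81 and 0.67, at which the power is only 89.2%, 89.3% and 89.5%.

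**4. Illustrations only** (unadjusted; these d values are not from the documents):

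| d | Power, 42 subjects | Power, 50 subjects | Total N for 90% |
|---|---|---|---|
| 0.5 | 35% | 41% | 172 |
| 0.8 | 72% | 79% | 68 |

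**5. Can the MANOVA reject with no SF-8 effect?** Assume six uncorrelated outcomes, 25 per arm, and an effect d on bowel movements alone. The joint test is a noncentral F with 6 and 43 degrees of freedom and noncentrality (25/2)d². It rejects in 46%, 69% and 98% of trials at d = 0.8, 1.0 and 1.5.

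**The case against.** Section 6.1 is not empty. It states an alpha, a power, an allocation ratio and a relative effect, and Section 6.2 names two methods. A reader might infer that the plan states no effect and no test at all; that goes too far. What is missing is an SF-8 difference and SD, and a designated test of the primary endpoint.

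A reader might also infer that 42 is an arithmetic error or that the trial is underpowered. The documents support neither. Step 1 shows that 42 can be right on the SIP, and nothing in the documents rules out an SF-8 difference of about one SD. The rows for d = 0.5 and 0.8 are benchmarks that nothing in the plan favours. Likewise, the MANOVA percentages depend on assumed effects and uncorrelated outcomes. They show that the joint test can reject for the wrong reason, not how often it will.

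Nor do the two uses of 50 imply a shortfall against 42. Under Section 2, 50 subjects complete and up to 75 may be enrolled; only Section 6.1's drop-out wording conflicts with that.

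One objection stands against the remedy. Adjusting for baseline SF-8 is safe only if baseline is collected before allocation is known. Sections 4.2.1 and 4.2.3 put baseline assessments after randomization, and Section 4.2.2 puts them before. In an open-label trial with a self-reported outcome, this must be settled first. The unadjusted figures do not depend on it.

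**Conclusion.** The concern holds as a gap in justification, not as proven underpowering. For the SF-8, 90% power with 42 subjects depends on an undisclosed condition: a standardized difference of about 1.03, unadjusted, at an assumed two-sided 0.05. The SIP citation does not supply that condition. Even on its own scale, the answer turns on how the 30% is read and on arm sizes that the documents do not give. The MANOVA of all outcomes does not answer Aim 1. The standardized differences are exact for a t-test with equal SDs; the adjusted ones also rest on the assumed correlations. This should be corrected.

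**What to change.** 1. **Section 6.1.** Replace the 90% claim with: *50 completers (25 per arm), two-sided 0.05, give 90% power for a standardized difference of 0.94 in the primary SF-8 score at day 28, and 80% for 0.81, unadjusted; with adjustment for baseline SF-8, 90% power needs about 0.91, 0.82 or 0.68 if the baseline-to-day-28 correlation is 0.3, 0.5 or 0.7 (assumed).* Add the expected SF-8 difference and SD in points, with a source or labelled as an assumption. If the expected difference is smaller than the detectable one, state the lower power.
2. **Section 6.2.** Name one SF-8 score as primary. Test it by linear regression of the day-28 score on arm, baseline SF-8 and the randomization stratum (WPAI ≤7 or >7, Section 4.2.2), with MANOVA supportive only. With baseline in the model, the treatment estimate is the same for the day-28 score (Section 1.2) and for change (Aim 1a).
3. **Sections 4.2.1, 4.2.2 and 4.2.3.** Reconcile the order, so that the baseline SF-8 used for adjustment is collected before allocation is known.
4. **Wording only.** Align the 50 in Section 6.1 with Section 2's 50 completers and cap of 75.

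**Cost.** Items 1, 2 and 4 change text only; item 3 may change the order of enrollment steps in practice. The stated power becomes conditional and less favourable, MANOVA becomes supportive, and the other SF-8 scores become secondary. If the sponsor's expected difference is well below the detectable one, the cap of 75 may not restore 90%: at the illustrative d = 0.5, unadjusted, 172 would be needed. The plan should then state the power it has.
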